15 STUDY-SPECIFIC MATERIALS

The Investigator will be provided with the following:

- eCRF:
- Forms and questionnaires for special assessments;
- Thermometers and measurements template;
- Study manuals.

16 ETHICAL ASPECTS

16.1 Study-Specific Design Considerations

On-going medical review will be performed by Medicago (or its designee) throughout the duration of the study; subjects will be given any new information that may affect their decision to continue participation in the study.

Blood samples will be collected from subjects for immunogenicity analysis, although not all will be analysed. Since blood sample collection is a minimally invasive procedure and the amount of blood collected will be a relatively small amount (Table 5), the benefits of obtaining this data outweigh the small level of risk associated with the collection of samples that may not require analysis.

16.2 Regulatory Ethics Compliance

16.2.1 Investigator Responsibilities

The Investigator is responsible for ensuring that the study is performed in accordance with the protocol, current International Conference on Harmonisation (ICH) guidelines on Good Clinical Practice (GCP), and applicable regulatory and country-specific requirements.

GCP is an international ethical and scientific quality standard for designing, conducting, recording, and reporting studies that involve the participation of human subjects. Compliance with this standard provides public assurance that the rights, safety, and well-being of study subjects are protected, consistent with the principles that originated in the Declaration of Helsinki, and that the study data are reliable.

16.2.2 Independent Ethics Committee or Institutional Review Board

Before the start of the study, the Investigator (or Medicago, where required) will provide the Independent Ethics Committee (IEC)/IRB with current and complete copies of the following documents (as required by local regulations):

- Final protocol and, if applicable, amendments to the protocol;
- Sponsor-approved ICF (and any other written materials to be provided to the subjects);
- IB (or equivalent information) and amendments/addenda;
- If applicable, Sponsor-approved subject recruiting materials;
- Information on compensation for study-related injuries or payments to subjects for participation in the study, if applicable;
- Investigator's *curriculum vitae* or equivalent information (unless not required, as documented by the IEC/IRB);
- Information regarding funding, name of the sponsor, institutional affiliations, other potential conflicts of interest, and incentives for subjects;
- Any other documents that the IEC/IRB requests to fulfill its obligation.

This study will be undertaken only after the IEC/IRB has given full approval of the final protocol, amendments (if any, excluding the ones that are purely administrative in nature, with no consequences for subjects, data, or study conduct), the ICF, applicable recruiting materials, and subject compensation programs, and Medicago (or its designee) has received a copy of this approval. This approval letter must be dated and must clearly identify the IEC/IRB and the documents being approved. In addition, the Investigator must wait for written confirmation from Medicago (or its designee) that the study can be started.

During the study, the Investigator (or Medicago [or its designee], where required) will send the following documents and updates to the IEC/IRB for their review and approval, where appropriate:

• Protocol amendments;

- Revision(s) to ICF and any other written materials to be provided to subjects;
- If applicable, new or revised subject recruiting materials approved by Medicago;
- Revisions to compensation for study-related injuries or payment to subjects for participation in the study, if applicable;
- New edition(s) of the IB and amendments/addenda;
- Summaries of the study at intervals stipulated in guidelines of the IEC/IRB (at a minimum, annually);
- Reports of AEs that are serious, unlisted/unexpected, and associated with the study drug (when applicable);
- New information that may adversely affect the safety of the subjects or the conduct of the study;
- Deviations from or changes to the protocol to eliminate immediate hazards to subjects;
- Reports of deaths of subjects under the Investigator's care;
- Notification if a new Investigator is responsible for the study at any of the sites;
- Development Safety Update Report and Line Listings, where applicable;
- Any other requirements of the IEC/IRB.

At least once a year, the IEC/IRB will be asked to review and reapprove this study. The reapproval should be documented in writing. At the end of the study, the Investigator (or Medicago [or its designee], where required) will notify the IEC/IRB of study completion.

16.2.3 Informed Consent

Each subject who participates in the study must first give written consent according to local requirements after the nature of the study has been fully explained, including the risks and requirements of the study. The consent form must be signed before performing any study-related activity. The consent form that is used must have been approved by regulatory authorities, Medicago, and the reviewing IEC/IRB. The informed consent should be in accordance with principles that originated in the Declaration of Helsinki, current ICH and GCP guidelines, applicable regulatory requirements, and Medicago policy. During the study, subjects will be given any new information that may affect their decision to continue their participation in the study. They will be told that their consent to participate is voluntary and that it may be withdrawn at any time, with no reason given, and without penalty or loss of benefits to which they would otherwise be entitled. Only subjects who are fully able to understand the risks, benefits, and potential AEs of the study and who provide their consent voluntarily will be enrolled.

16.2.4 Privacy of Personal Data

The collection and processing of personal data from subjects enrolled in this study will be limited to those data that are necessary to support the development, registration, and future marketing of the investigational product. The data must be collected and processed with adequate

precautions to ensure confidentiality and compliance with applicable data privacy protection laws and regulations. Appropriate technical and organizational measures to protect the personal data against unauthorized disclosures or access, accidental or unlawful destruction, or accidental loss or alteration must be in place. Medicago (or its designee) personnel whose responsibilities require access to personal data agree to keep the identity of study subjects confidential.

17 ADMINISTRATIVE REQUIREMENTS

17.1 Protocol Amendments

Neither the Investigator nor Medicago will modify this protocol without a formal amendment. All protocol amendments must be issued and approved by Medicago and signed and dated by the Investigator. Protocol amendments must not be implemented without prior IEC/IRB approval or when the relevant competent authority has raised any grounds for non-acceptance, except when necessary, in order to eliminate an immediate hazard to the subjects, in which case the amendment must be promptly submitted to the IEC/IRB and relevant competent authority. Documentation of amendment approval by the Investigator and IEC/IRB must be provided to Medicago or its designee.

Note that administrative changes may be implemented without prior IRB approval; however, the Investigator or Medicago, as applicable, must notify the IRB of any administrative change and ensure that IRB acknowledges receipt of the administrative changes.

The Investigator is responsible for notifying the IRB of all protocol amendments and ensuring that the IRB has approved any amendments when local IRBs are used. When a central IRB is used, Medicago or its designee will inform the IRB on behalf of the sites.

During the course of the study, in situations where a departure from the protocol is unavoidable, the Investigator or other physician in attendance will contact the appropriate Medicago representative or its designee (see Contact Information pages provided separately). Except in emergency situations, this contact should be made before implementing any departure from the protocol. In all cases, contact with Medicago or its designee must be made as soon as possible to discuss the situation and to agree on an appropriate course of action. The data recorded in the eCRF and source documents will reflect any departure from the protocol, and the source documents will describe this departure and the circumstances that made a deviation necessary.

17.2 Regulatory Documentation

17.2.1 Regulatory Approval/Notification

This protocol and any amendment(s) must be submitted to the appropriate regulatory authorities in each respective country, as applicable. A study may not be initiated in the respective country until all local regulatory requirements are met.

17.3 Source Documentation

At a minimum, source documentation must be available for the following information:

medicago⁻

- Subject identification, eligibility, and study identification;
- ICF discussion and date of informed consent;
- Dates of visits:
- Results of safety and study procedures as required by the protocol;
- Record of all reactions, AEs, and associated follow-ups;
- Concomitant medication;
- Drug receipt, dispensing, and return records;
- Study drug preparation and administration information;
- Date of study completion and reason for early discontinuation of study drug or withdrawal from the study, if applicable.

It is recommended that the author of an entry in the source documents be identifiable.

At a minimum, the type and level of detail of source data available for a study subject should be consistent with that commonly recorded at the site as a basis for standard medical care. If Investigator judgement was used in the determination of eligibility, an explanation for inclusion of the subject in the study must be provided in the source documents. Specific details required as source data for the study will be reviewed with the Investigator before the study and will be described in the monitoring guidelines (or other equivalent document).

17.3.1 Diary and Memory Aid

Subjects will be provided with a diary (manual or electronic) in which to record AEs and other safety information. Subject diaries are considered source documents; the manual diary will be returned by the subject to the site at the Day 28 visit and kept with each subject's study chart. In the event the manual diary is lost by the subject, information collected by the coordinator or designee and information recalled by the subject will serve as the source data for this subject. The recalled information will be captured in the source documents. The electronic diary will capture information directly in the electronic data capture system.

Corrections to data entered by the subject in the diary should only be performed by the subject him/herself, when possible. Clarifications can be made in the comment section of the manual diary by the study personnel if the subject is not present onsite to make the correction him/herself.

Subjects will be provided with memory aids (manual or electronic) to record information on unsolicited AEs, SAEs, AESIs, MAAEs, NOCDs, AEs leading to withdrawal, and reportable concomitant medications from the Day 0 to Day 28, Day 29 to Day 182, and Day 183 to the end of the study (Day 365). These memory aids will be collected by the site and are intended to be used by the subject to help them in reporting this information to site staff during phone contacts and clinical site visits. The electronic memory aids will capture information directly in the electronic data capture system.

17.4 Case Report Form Completion

An eCRF will be provided for each subject who is randomized and receives a dose of study vaccine. Screening failures will also be entered in an eCRF; data entered should include date of birth and reason for screening failure.

Data must be entered into the eCRFs in English. The Investigator must verify that all data entries in the eCRFs are accurate and correct. All eCRF entries, corrections, and alterations must be made by the Investigator or other authorized study-site personnel.

Please refer to the eCRF completion guidelines for details of data entry requirements.

17.5 Quality Control (Study Monitoring)

In accordance with applicable regulations, GCP, and Medicago (or its designee) procedures, the site will be contacted prior to the study start to review the protocol and study requirements with the clinical study staff. Medicago (or its designee) will review their responsibilities to satisfy regulatory, ethical, and company (Medicago) requirements.

The Investigator or institution, if applicable, will authorize and provide direct access to all relevant documents to allow review of the appropriate conduct of the study by Medicago's (or its designee's) monitor. The Investigator(s) must allocate their time and the time of their staff to the monitors, discuss any findings or issues, and take appropriate actions to maintain the quality and integrity of the study data and conduct.

Protocol deviations will be reviewed by Medicago (or its designee) to identify any non-compliances likely to have a significant effect on the safety and rights of a subject or the reliability and robustness of the data generated. These deviations will be included in the clinical study report.

17.6 Quality Assurance

To ensure compliance with GCP and all other applicable regulatory requirements, Medicago (or its designee) may conduct quality assurance assessments and/or an audit of the site. Regulatory agencies may conduct regulatory inspections at any time during or after completion of the study. If an audit or an inspection is conducted, the Investigator and/or institution (if applicable) must agree to grant auditors or inspectors direct access to all relevant documents and to allocate their time and the time of their staff to discuss the conduct of the study and any findings or issues, and to implement corrective and/or preventative actions to address any findings or issues identified.

17.7 Record Retention

Following closure of the study, the Investigator must maintain all site study records in a safe and secure location. The records must be easily accessible when needed (e.g. for a Medicago [or its designee] audit or regulatory inspection) and must be available for review in conjunction with assessment of the facility, supporting systems, and relevant site staff.

When permitted by local laws and regulations or institutional policy, some or all of the records

may be maintained in a format other than a hard copy (e.g. scanned electronic). The Investigator must ensure that all reproductions are legible and are a true and accurate copy of the original.

The Investigator must follow the time period for retaining the site records in order to comply with all applicable regulatory requirements. The minimum retention time will meet the strictest standard applicable to a particular site, as dictated by local laws and regulations, Medicago (or its designee) standard operating procedures (SOPs), and/or institutional requirements. The Investigator must contact Medicago (or its designee) prior to the disposal of any study documents at the end of the retention period.

If the responsible Investigator retires, relocates, or, for any other reason, withdraws from the responsibility of keeping the study records, custody must be transferred to another qualified person who will accept the responsibility and is approved by Medicago. Medicago (or its designee) must be notified in writing of the name and address of the new custodian. Under no circumstance shall the Investigator relocate or dispose of any study documents without having obtained prior written approval from Medicago (or its designee).

If it becomes necessary for Medicago or the appropriate regulatory authority to review any documentation relating to this study, the Investigator (or new custodian) must permit access to such reports in a timely manner.

17.8 Study Completion/Termination

17.8.1 Study Completion

The study will be considered to be completed when the last contact with the last subject participating in the study has occurred. The final data from the investigational site will be sent to Medicago (or designee) after completion of the final subject visit at that site. Investigational sites will be closed after study completion. An investigational site is considered closed when all required documents and study supplies have been collected, all data have been entered, monitored, locked, and signed and a site closure visit has been performed.

17.8.2 Study Termination

Medicago (or its designee) reserves the right to close the investigational site or terminate the study at any time for any reason at the sole discretion of Medicago. Investigational sites will be closed after study termination once Medicago (or its designee) has completed all study related tasks. Reasons for the early closure of an investigational site by Medicago (or its designee) or the Investigator may include, but are not limited to:

- Failure of the Investigator to comply with the protocol, Medicago's (or its designee's) procedures, or GCP guidelines;
- Inadequate recruitment of subjects by the Investigator;
- Discontinuation of further drug development.

The Investigator may initiate site closure at any time, provided there is reasonable cause and

sufficient notice is given in advance of the intended closure.

Site closure following an Investigator request can only be performed when all active study subjects have completed the study period, Medicago (or its designee) has collected all required documents and study supplies, and all data have been entered, monitored and locked.

17.9 Registration of Clinical Studies and Disclosure of Results

Study information from this study will be posted on publicly available clinical trial registries in countries where applicable and will include information required by law. In addition, the results summary will be posted to the same clinical trial registries, to the extent specified by law, and will include information required by regulatory authorities.

17.10 Publication Policy

The data derived from this study are the property of Medicago and cannot be published without prior authorization from Medicago. Any publication activities (i.e. preparation and submission of abstracts and manuscripts) will be at the discretion of Medicago.

Any proposed publication regarding this study, not prepared by Medicago personnel, must be provided to Medicago for comments and review at least 45 days prior to its intended publication. The proposed publication shall not include any confidential information or protected information to preserve Intellectual Property rights; any such information must be removed from the proposed publication.

19 APPENDICES

The clinical documents included in the appendices are meant as examples only; the actual documents used during the trial may differ slightly.

19.1 Appendix 1 – Sample Ruler to Measure Local Adverse Events

Site Adverse Event Measuring Ruler

	or redness and swelling where the vaccine was given
Grade 0	None or less than 25 mm
Grade l	Between 25 mm and 50 mm
Grade 2	Between 51 and 100 mm
Grade 3	More than 100 mm
Grade 4	skin/tissue loss at the injection site (blister or ulcer
	formation) of any size

19.2 Appendix 2 – Subject Diary Sample Pages

	DIARY (DAY 0 to DAY 7)					
Study Name	A Randomized, Partially-Blinded, Active Comparator-Controlled, Dose-Ranging, Safety, Tolerability, and Immunogenicity Phase 1/2 Study of an Adjuvanted Seasonal Recombinant Quadrivalent VLP Influenza Vaccine in Adults 65 Years of Age and Older					
Protocol Number	CP-PRO-AdjQVLP-020					
	Medicago USA Inc.					
Sponsor	[name]					
Clinical site Address	NOTOS					
Principal Investigator Name	[name] SAMPLE ONLY. DO NOT USE SAMPLE					
Clinical Research Coordinator	MPLE					
24-hour Emergency Number	SAL					

DIARY (DAY 0 to DAY 7) INSTRUCTIONS

- You should fill in your Diary at approximately the same time, preferably in the evening.
- You will need to refer to this Diary during the Telephone Calls (on Day 1 and Day 8).
- You need to bring this Diary with you at the Day 3 and Day 28 visits.
- Fill in the Day 0 to Day 7 tables EVERY DAY for the first 7 days after you receive your vaccine dose.
- Fill in each day's column by entering the WORST grade for each symptom that you had during the period.
- Grayed out sections are to be left blank and will be completed by the site personnel.
- · To complete this document, use blue or black ink. No pencil or liquid paper is allowed.
- If you made a mistake, cross out the incorrect information, initial and date, and write the correct answer beside.
- · Date should be recorded with 2 digits for day, 3 letters for month and 4 digits for year

January	JAN	April	APR	July	JUL	October	OCT
February	FEB	May	MAY	August	AUG	November	NOV
March	MAR	June	JUN	September	SEP	December	DEC

TEMPERATURE:

- To record the temperature, use the thermometer you were given at the clinic. Do not drink, eat food or smoke prior to taking your temperature.
- You should take your temperature for the first 7 days following vaccination at approximately the same time each evening and at any other time if you feel feverish.
- You will need to record the highest temperature of the day on page 4.
- If your temperature is 38°C or 100.4°F or higher, you are allowed to take over-the-counter antipyretics (e.g., acetaminophen/paracetamol, aspirin, naproxen, or ibuprofen) and you should increase the frequency of temperature measurements to approximately every 4 hours, until you don't have a fever anymore.
- Medication intake needs to be documented on the Memory Aid and will be reviewed by the site personnel.

DIARY (DAY 0 to DAY 7) INSTRUCTIONS
SYMPTOMS:
• Complete the table referring to the following periods:
o For the 1st column: the period between the vaccination and the 30 minutes post-vaccination;
o For the 2 nd column: the period between the last evaluation (30 minutes post-vaccination) and
the evening;
 For the remaining columns: the period since the previous evaluation of the symptoms.
 If the symptom is not present, indicate 0.
 If the symptom is present, a grade should be indicated.
 Evaluate the grade of all other symptoms according to the definitions:
○ 0= No symptom
 1= Does not interfere with activity
 2= Repeated use of non-narcotic pain reliever (e.g. Advil, Tylenol) >24 hours or interferes
with activity but does not require medical intervention
o 3= Any use of narcotic pain reliever (e.g. codeine, morphine) or prevents daily activity
and require medical intervention
 4= Visit to Emergency room or hospitalization
• List any other problems (not listed on pages 4 to 6) on the Memory Aid (Day 0 to Day 28) page "side
effects (symptoms)".
 Symptoms listed on pages 4 to 6 which persist longer than 7 days after study vaccine administration
must also be listed on the Memory Aid (Day 0 to Day 28) page "side effects (symptoms)".
must also be listed on the inteniory Aid (Day o to Day 20) page side effects (symptoms).
You received the study vaccine on:
dd mmm yyyy hh mm
Initial and date:
dd mmm yyyy

	DIARY (DAY 0 to DAY 7)											
Day 0 to Day 7		30 min, Post-dose	Evening, day of dose	1 st Day after dose	2 nd Day after dose	3 rd Day after dose	4 th Day after dose	5 th Day after dose	6 th Day after dose	7 th Day after dose		
Date (dd-mmm-yyyy)												
Onal Tampanatura	°C / °F											
Oral Temperature	Causality											
Redness where	Grade											
the injection was	Causality											
given	Use the measuring tool given to you at the site to estimate the size of the red area around the injection site and indicate the grade above.											
Swelling where	Grade											
the injection was	Causality											
given	Use the measuring tool given to you at the site to estimate the size of the swollen area around the injection site and indicate the grade above.											
	Grade											
Pain at vaccine injection site	Causality											
injection site	0= No symptom; 1= Does not interfere with activity; 2= Repeated use of non-narcotic pain reliever >24 hours or interferes with activity; 3= Any use of narcotic pain reliever or prevents daily activity; 4= Visit to Emergency room or hospitalization.											
Comments:	Comments:											
MD signature and da	te:			dd	mmm	уууу						

Confidential Information

medicago^{*}

	DIARY (DAY 0 to DAY 7)											
Day 0 to Day 7		30 min, Post-dose	Evening, day of dose	1 st Day after dose	2 nd Day after dose	3 rd Day after dose	4 th Day after dose	5 th Day after dose	6 th Day after dose	7 th Day after dose		
Headache	Grade											
пеадаспе	Causality											
	symptom; 1= D se of narcotic pa								erferes with a	ctivity; 3=		
Muscle aches	Grade											
Muscle acnes	Causality											
	symptom; 1 = D	oes not interf	ere with activ	ity; 2= Interfe	eres with activ	vity; 3= Preve	ents daily acti	vity; 4= Visit	to Emergenc	y room or		
Fatigue	Grade											
Taugue	Causality											
	symptom; 1 = D dization.	oes not interf	ere with activ	ity; 2= Interfe	eres with activ	vity; 3= Preve	ents daily acti	vity; 4= Visit	to Emergency	y room or		
Taint ashaa	Grade											
Joint aches	Causality											
GRADES 0= No symptom; 1= Does not interfere with activity; 2= Interferes with activity but does not require medical intervention; 3= Prevents daily activity and requires medical intervention; 4= Visit to Emergency room or hospitalization.												
Comments:												
MD signature and dat	e:			dd	mmm y	 ууу						

Confidential Information

	DIARY (DAY 0 to DAY 7)											
Day 0 to Day 7		30 min, Post-dose	Evening, day of dose	1 st Day after dose	2 nd Day after dose	3 rd Day after dose	4 th Day after dose	5 th Day after dose	6 th Day after dose	7 th Day after dose		
Chills	Grade											
Cillis	Causality											
Feelings of	Grade											
general discomfort or uneasiness	Causality											
Feeling of	Grade											
swelling in the neck	Causality											
Feeling of	Grade											
swelling in the axilla (armpit)	Causality											

GRADES 0= No symptom; 1= Does not interfere with activity; 2= Interferes with activity but does not require medical intervention; 3= Prevents daily activity and requires medical intervention; 4= Visit to Emergency room or hospitalization.

Comments:	
I confirm I have reviewed the 3 pages of solicited symptoms Comments section on this page.	s and evaluated the causalities when needed. I confirm I have reviewed all entries in the
MD signature and date:	dd mmm yyyy

Confidential Information

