10.2.1.1 Solicited Local and Systemic AEs

Subjects will be monitored for both solicited local AEs (erythema, swelling, and pain at the injection site) and solicited systemic AEs (fever, headache, fatigue, muscle aches, joint aches, chills, a feeling of general discomfort, swelling in the axilla, and swelling in the neck) from the time of vaccination through Day 7. While the subjects remain in the clinic following vaccine administration (at least 30 minutes), staff will monitor them for local and systemic AEs; after release from the clinic facility, from the evening of Day 0 to the evening of Day 7, subjects will measure and record their local and systemic AEs in their diary.

The intensity of the solicited local and systemic AEs will be assessed by the subject, documented in the diary, and graded as: mild (1), moderate (2), severe (3) or potentially life threatening (4) (please refer to Table 6). The causal relationship of all solicited local and systemic AEs will be considered related.

The Investigator should assess solicited AEs and determine if any meet the criteria for SAE. Any solicited local or systemic AEs that meet the criteria for SAE should be reported to the Sponsor within 24 hours (Section 13.1.6) and entered as an SAE in the eCRF.

Table 6 Severity Grades for Solicited Local and Systemic AEs

Symptoms	Severity								
	None Gr.		Grade 2 (Moderate)	Grade 3 (Severe)	Grade 4 (Potentially life- threatening)				
Injection Site AEs (Lo	cal AEs)		1		•				
Erythema (redness)	< 25 mm	25 - 50 mm	51 - 100 mm	> 100 mm	Necrosis or exfoliative dermatitis				
Swelling	< 25 mm	25 - 50 mm and does not interfere with activity	51 – 100 mm or interferes with activity	> 100 mm or prevents daily activity	Necrosis				
Pain	None	Does not interfere with activity	Repeated use of non-narcotic pain reliever for more than 24 hours or interferes with activity	Any use of narcotic pain reliever or prevents daily activity	Results in a visit to emergency room (ER) or hospitalization				
Solicited Systemic AE	S								
Fever (°C or °F)	< 38.0 °C < 100.4 °F	38.0 - 38.4 °C 100.4 - 101.1 °F	38.5 - 38.9 °C 101.2 - 102.0 °F	39.0 - 40.0 °C 102.1 - 104.0 °F	> 40.0 °C > 104.0 °F				
Headache	None	No interference with activity	Repeated use of non-narcotic pain reliever for more than 24 hours or some interference with activity	Significant; any use of narcotic pain reliever or prevents daily activity	Results in a visit to emergency room (ER) or hospitalization				

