10.2.2 Safety Endpoints

10.2.2.1 Primary Endpoints

- Occurrences, intensity, and relationship to vaccination of immediate AEs (30 minutes post-vaccination);
- Occurrences and intensity of solicited local and systemic AEs (for seven days following study vaccine administration);
- Occurrences, intensity, and relationship of unsolicited AEs for 28 days following study vaccine administration;
- Number and percentage of subjects with normal and abnormal, clinically significant urine, haematological and blood biochemistry values, and urinalysis at Days 0, 3, and 28;

- Occurrences of SAEs, AEs leading to withdrawal, AESIs, MAAEs, NOCDs, and deaths up to Day 28;
- Occurrences of SAEs, AEs leading to withdrawal, AESIs, MAAEs, NOCDs, and deaths from Day 29 up to Day 182;
- Occurrences of SAEs, AEs leading to withdrawal, AESIs, MAAEs, NOCDs, and deaths from Day 183 up to the end of the study (Day 365).

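### The sample ruler and diary depart from the Table 6 severity scale in limited places: injection-site swelling, local Grade 4, and the diary instruction page's Grade 3

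*Protocol*

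**What the plan says.** Protocol 10.2.2.1 lists "Occurrences and intensity of solicited local and systemic AEs (for seven days following study vaccine administration" among the primary safety endpoints. Protocol 10.2.1.1 makes the subject the grader: "The intensity of the solicited local and systemic AEs will be assessed by the subject, documented in the diary, and graded as" mild through potentially life-threatening, with reference to Table 6. The same section treats every solicited event as vaccine-related.

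For swelling, Table 6 sets Grade 2 at "51 – 100 mm or interferes with activity" and Grade 3 at "> 100 mm or prevents daily activity". Grade 1 requires 25–50 mm with no interference. Grade 4 is necrosis for swelling and "Necrosis or exfoliative dermatitis" for erythema. SAP Table 2 carries the same Grade 3 rule for swelling. Protocol 10.1.4.3 gives subjects a template for measuring redness and swelling in millimetres, tells them to record the results, and refers local severity to Table 6.

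The sample forms read differently:

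- **Ruler (Appendix 1).** One scale serves both redness and swelling. Grades 0 to 3 are size bands only. Grade 4 begins "skin/tissue loss at the injection site (blister or ulcer" and goes on to include such formation whatever its size.
- **Diary, swelling row (Appendix 2).** The subject uses the measuring tool to "estimate the size of the swollen area around the injection site and indicate the grade above". The row holds a grade and a causality entry.
- **Diary, instruction page (Appendix 2).** It says "Evaluate the grade of all other symptoms according to the definitions" and then gives one merged list, in which a symptom that stops daily activity must also need medical intervention to reach Grade 3.

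Protocol Section 19 describes the appendix forms as examples from which the real ones may differ a little. SAP 9.2 makes the e-diary the principal tool and paper the back-up.

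**The concern.** The safety tables will be read on the Table 6 scale, but the grade is assigned by a subject working from the diary and ruler. Where those forms use a different rule, the reported intensity follows the form and not the table.

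Grades also affect conduct. Under Protocol 13.1.12, two or more subjects in one group with the same or similar Grade 3 or higher related event may halt the study. The sample IDMC summary (Appendix 4) tabulates solicited Grade 3–4 events. Subjects are told to contact the site for events above Grade 2 (Protocol 10.1.4.3). A swelling recorded too low is missed at each of these points. A local reaction put into Grade 4 by loose wording would do the opposite.

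**Working it through.** The plan gives no figure to reproduce (SAP 4.1 states that no sample-size calculation was done). The check is a comparison item by item, followed by one illustration.

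**1. Swelling, Grades 1–3.** Inputs: Table 6, and the ruler bands of 25–50, 51–100 and over 100 mm.

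| Swelling | Table 6 grade | Ruler/diary grade | Shortfall |
|---|---|---|---|
| 25–50 mm, no interference | 1 | 1 | 0 |
| 25–50 mm, interferes with activity | 2 | 1 | 1 |
| 25–50 mm, prevents daily activity | 3 | 1 | 2 |
| 51–100 mm, prevents daily activity | 3 | 2 | 1 |
| Over 100 mm | 3 | 3 | 0 |
| Under 25 mm, limits activity | unclear | 0 | not determinable |

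The last row is unclear because Table 6 lists under 25 mm as no event, yet its Grade 2 and 3 entries allow function alone to qualify.

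**2. Local Grade 4.** Table 6 has necrosis, or exfoliative dermatitis for erythema. The ruler has skin or tissue loss, explained in brackets as blister or ulcer formation, with no size limit. The two may be meant to agree, but they are not the same words.

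**3. Instruction page, Grade 3.** The printed grids for pain, muscle aches and fatigue have no medical-intervention condition. Nor does Table 6 for those three or for headache. The instruction page adds one, so it raises the threshold for four symptoms. The joint aches, chills, malaise, axilla and neck grids do carry that condition, and so does Table 6.

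**4. How much agrees.** There are 3 local + 9 systemic = 12 solicited events. Fever is entered as a temperature, and nine symptoms have grids consistent with Table 6, so 1 + 9 = 10 of 12 can be graded correctly. The headache grid is only partly legible in the text available; its visible part agrees. The other two are swelling (items 1 and 2) and redness (Grade 4 only; its size bands match).

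**5. Later correction.** The physician sign-off in the diary covers review of entries, causality and comments. The SAP 9.2 rule on investigator assessment chooses between duplicate paper and electronic records. Protocol 10.2.1.1 has the Investigator judge seriousness. None of these describes regrading to Table 6.

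**6. Illustration for the halt criterion, with assumed rates.** From the documents: 40 subjects per group and a trigger of two or more. Assumed: a true Grade 3 or higher swelling rate p, half of it qualifying by function alone, so that size-only grading sees p/2. The chance of at least two subjects is 1 − (1 − p)^40 − 40p(1 − p)^39.

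- p = 5%: 1 − 0.1285 − 0.2706 = 0.60. At 2.5%: 1 − 0.3632 − 0.3725 = 0.26.
- p = 2%: 0.19 falls to 0.06.
- p = 10%: 0.92 falls to 0.60.

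The documents give neither the rate nor the share qualifying by function. These figures show sensitivity only and forecast nothing.

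**The case against.** The strongest reply is that these are sample pages. Section 19 says the fielded forms may differ, the e-diary is the principal tool and its text is not in the documents, and Protocol 10.1.4.3 has subjects measure in millimetres and grade to Table 6. Calls on Days 1 and 8 and diary reviews on Days 3 and 28 offer chances to notice a disabling swelling. Each grid prints its grades beside the row being filled in, so the merged list may have little influence. All of this stands, and it limits what can be said about the data actually collected. It does not remove the contradiction between the protocol's scale and the only instruments it shows.

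A reader might infer more than the documents support:

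- **That the diary does not apply Table 6, so reported intensity is not the defined endpoint.** Ten of the twelve events can be graded to Table 6.
- **That any blister is Grade 4.** The ruler's leading term is skin or tissue loss, and the bracket can be read as a lay explanation of it.
- **That swelling can be misgraded by three grades.** This needs a swelling under 25 mm, where Table 6 is itself unclear.
- **That the error cannot be undone.** The sample page has no millimetre or activity field, but what the e-diary stores is unknown.
- **That the adjuvanted group is favoured.** Protocol 1.3.1.1 expects more reactogenicity with AS03, mostly mild to moderate, but says nothing about function-limiting swelling.

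**Conclusion.** The point holds in a limited form. The sample ruler and diary conflict with Table 6 and SAP Table 2 on swelling where function decides the grade, and in the wording of local Grade 4. The instruction page conflicts at Grade 3 with the diary's own pain, muscle-ache and fatigue grids, and with Table 6 for those items and headache.

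The definite size is a shortfall of one or two grades for a 25–50 mm swelling that limits activity, and one grade for a 51–100 mm swelling that prevents daily activity. How many subjects this touches cannot be estimated from the documents. The conclusion assumes that the fielded forms follow the samples; if the e-diary already asks about activity, the swelling point falls away for its records. It should be put right because the affected grades belong to a primary safety endpoint and to the halt criterion, and no described step corrects them.

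**What to change.** - Reconcile Table 6, SAP Table 2, the ruler, and the paper and electronic diaries so that one set of definitions applies, including a single wording for Grade 4 redness and swelling. Which wording stands is for the sponsor to decide.
- Have the diary capture what the swelling grade needs, namely diameter in millimetres and effect on activity (none, interferes, prevents), and derive the grade in the database. State how a swelling under 25 mm that limits activity is graded.
- Replace the merged grade list on the instruction page with a reference to the symptom-specific grids.
- If the data are already collected, check the e-diary wording and state in the SAP and study report which scale produced the swelling and local Grade 4 results.

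The cost is form edits, a short derivation and at most one extra diary field a day. If collection is complete, it is a check of the e-diary and a sentence in the SAP and the report.
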